### 4.7.7 Sensitivity Analyses

As outcome comprises correlated survival data due to possible recurrent events, frailty model will be estimated to compare the outcome between the treatment arms.

### 4.7.8 Subgroup Analyses

None planned.

## 4.8 Additional Analyses

Any further future analyses not specified in the analysis protocol will be exploratory in nature and will be documented in a separate statistical analysis plan.

## 4.9 Sample size

The estimation of sample size is performed for primary outcome, time from start of continuous infusion until the last dose adjustment within the 48-hour period, and is based on the following assumptions: normal distribution within each treatment arm, difference in time from start of infusion to final dose adjustment between the IV and SC treatment arm of minimum 12 hours (assumed clinically significant), and SD of 12 hours in each arm. To show that the difference between the groups is statistically significant at the significance level of 5% with 90% power, using a two-sided independent samples t-test, the minimum number of patients is estimated to be 23 in each arm, total 46. Expecting a 25% dropout rate, 30 subjects need to be included in each group.

---

## **5 Safety Analyses**

The number (and percentage) of patients experiencing each AE/SAE will be presented for each treatment group categorized by severity. For each patient, only the maximum severity experienced of each type of AE will be displayed. The number (and percentage) of occurrences of each AE/SAE will also be presented for each treatment arm.

The Data Monitoring and Safety Committee (DMSC) will be informed of serious adverse events. The committee will if necessary, make decisions about terminating the trial before completed inclusion.

Study-specific safety measurement during intervention period:

Repeated measurement of saturation (every 12 hours), sedation level and respiration frequency (every 2 hour and after each bolus dose) will be assessed by linear mixed models mirroring the approach used for the analysis of secondary outcome c).

Opioid side effects score, mean (SD) at 24 and 48 hours will be presented for each treatment group and compared by an independent samples t-test

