### 1.3.2 Exploratory research question (if applicable)

Exploratory objectives include but are not restricted to following research questions:

- i. Are there any group differences in change of ESAS score other than pain?
- ii. What is the Patient Global Impression of Change in the two groups?
- iii. Is there a difference between SC and IV group in morphine concentration in steady state\*?  
(\*>24 hours after start of infusion and >2 hours since last bolus dose)
- iv. Is there a relationship between BMI and pharmacokinetic analyzes in the SC group?
- v. How does respiration frequency (RF) and oxygen saturation change during the intervention?  
Are there any differences between the SC and IV group?
- vi. What is the change in opioid side effect score in the two groups at 0, 24 and 48 hours
- vii. What is the change in opioid dose (in OME) from start of titration to 48 hours
- viii. What is the change in opioid dose (in OME) during follow up period
- ix. What are the complications to SC line and IV line
- x. What is the study population survival censored at 4 weeks

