### **Secondary**

- b. The number of bolus doses after 24 and after 48 hours in the two groups are different
- c. The pain score in the groups differ during the 48-hour period
- d. Time from bolus dose to clinically significant pain relief (change of 2 on 0-10 NRS) differ between the SC and IV group

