## STATISTICAL ANALYSIS PLAN for SIM-study

---

Time	Screening Period	Treatment Period		
	Within 24 hours of treatment	Baseline/start of treatment Between 11 am and 3 pm	12, 24, 36, and 48 +/- 2 hours	24 +/- 2; 48 +/- 2 hours
Inclusion/exclusion Evaluation	X			
Height, Weight	X			
Medical History	X			
Prior analgesic treatment	X			
Current medication	X			
Vital signs		X	X	
ESAS-revised		X	X	
EORTC QLQ-C30		X		X(at 48 +/- 2 hours)
EAPC basic data set	X			
Opioid side effects		X		X
Patient Global Impression of Change				X (at 48 +/- 2 hours)
Blood samples 	X			
Treatment administration/dispensation		X	X	
Adverse event		X	X	X
Clinician's decision to continue ongoing treatment or to change treatment				X
Record of concomitant medication		X	X	X
Morphine dose		X	X	X
Hospitalization				
Survival				
Complications to IV line				
Need for switch SC to IV				
Reason for withdrawal				

1. Blood pressure, pulse, temperature, sedation level, respiratory rate

2. CRP, Hb, WBC (incl. differential counting), PLT, Na, K, Ca, creatinine, ASAT, ALP, γGT, INR, albumin, bilirubin

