## **4 Outcome Definitions**

### **4.1 General Definitions and Derived Variables**

#### **4.1.1 NRS – Numeric Rating Scale**

NRS is a widely used, standard one-dimensional scale from 0 to 10 for patient self-reporting of pain (Breivik et al., 2008). NRS is collected as part of ESAS at 0, 12, 24, 36, and 48 hours. Exact recording time is registered. NRS is also recorded before and after any bolus dose administration. A change of NRS of 2 or more after a bolus dose is considered as clinically significant change. A mean NRS score difference of 1-2 is typically considered clinically significant when treatment arms are compared.

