## 4.6 Methods for Continuous Secondary Outcomes

### 4.6.1.1 *The pain score recorded every 12 hours during the 48 hours period. (Outcome c)*

Linear mixed model with random effects for patients and slopes will be estimated to assess the difference between the groups in overall trend in pain score. The model will include fixed effects for (possibly non-linear polynomial for) time, group dummy and the interaction between the two. Post hoc analyses will be performed to assess between-group differences at each time point as well as within-group changes.

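### Respiration and sedation readings taken on schedule and after boluses go into one mixed model with no term for reading type, so a false time trend or route difference can appear if bolus use shifts

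*SAP*

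**What the plan says.** SAP section 5 (Safety Analyses) names the data and the method in one sentence: "sedation level and respiration frequency (every 2 hour and after each bolus dose) will be assessed by linear mixed models mirroring" the analysis of secondary outcome c. Saturation is in the same sentence, but is read every 12 hours only. Section 5.3 refers back to section 5 for respiration frequency and adds nothing.

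The model to be mirrored is in section 4.6.1.1. Its random part is "Linear mixed model with random effects for patients and slopes will be estimated". Its fixed part is: "The model will include fixed effects for (possibly non-linear polynomial for) time, group dummy and the interaction between the two". There is no term for reading type or for time since the last bolus. The outcome it was written for is "The pain score recorded every 12 hours during the 48 hours period". Pain is also scored around boluses (section 4.1.1: "NRS is also recorded before and after any bolus dose administration"), but those scores are not part of outcome c.

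Exploratory question v (section 1.3.2) asks "How does respiration frequency (RF) and oxygen saturation change during the intervention" and whether the routes differ. Among the secondary alternative hypotheses in section 2.4.1.2 is: "The number of bolus doses after 24 and after 48 hours in the two groups are different".

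Table 1 schedules vital signs at baseline and at 12, 24, 36 and 48 hours. Its first footnote, which evidently belongs to that row, lists "Blood pressure, pulse, temperature, sedation level, respiratory rate".

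**The concern.** Outcome c is measured at times fixed in advance. Respiration frequency and sedation level are measured partly at fixed times and partly when a patient has just taken a bolus. The number and timing of the second kind depend on bolus use, which arises after randomisation and which the trial itself compares between arms.

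A model with only time and group treats every reading as a sample of the same quantity. If post-bolus readings have a different level, a change in the mix of readings is fitted as a change in respiration or sedation. Random patient intercepts and slopes do not remove this, because the mix can change within a patient over time. A polynomial in time does not remove it either; it only follows the changing mix more closely.

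At stake is the answer to question v for respiration frequency, and the parallel safety analysis of sedation level. The pooled model could show a trend or route difference that does not exist, or mask one that does.

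**Working it through.** **Inputs from the SAP.** Readings every 2 hours, so 12 scheduled readings per day and 48/2 = 24 over the intervention period; one further reading per bolus; 30 patients per arm (section 4.9); two-sided 5% level (section 2.4.2). The SAP gives no figure for this analysis that could be reproduced. Its only computed figure, 23 per arm for the primary outcome, reproduces (two-sided t-test, difference 12 h, SD 12 h, 90% power: 22.02, rounded up). It matters here only as the source of the 30.

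**Inputs assumed.** Bolus rates and the size of any post-bolus shift.

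**Step 1: share of triggered readings.** With b boluses per day, share = b/(b + 12).
- b = 4: 4/16 = 25%
- b = 8: 8/20 = 40%
- b = 12: 12/24 = 50%

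**Step 2: expected artefact.** Artefact = difference in share x post-bolus shift.
- Use falling from 12 to 4 per day, shift -1.5/min: (0.25 - 0.50) x (-1.5) = +0.375/min from start to end with no true change. At -3/min: +0.75/min.
- Constant use, IV 4 and SC 8 per day, shift -1.5: (0.40 - 0.25) x (-1.5) = -0.225/min between arms.
- Use falling in both arms, from 3 to 1 (IV) and from 6 to 1 (SC) boluses per 12 h against 6 scheduled readings: shares go from 3/9 = 33% and 6/12 = 50% to 1/7 = 14% in both. A shift of 2/min in size moves the means by 0.38 and 0.71, a false route difference of 0.33/min. At 4/min it is 0.67.
- Shift zero, or constant and equal use: zero.

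**Step 3: what the planned model would report.** I simulated respiration frequency with no true time or route effect: 30 per arm without dropout, between-patient SD 2/min, slope SD 0.02/min per hour, residual SD 1.5/min, bolus use varying between patients, 300 runs per scenario. The model had time, group, their interaction, and random intercepts and slopes. Entries are the mean false effect (per minute; trends over 48 h) and the percentage of runs significant at 5%, with all readings pooled.

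| Boluses/day | Shift | Time trend (IV) | Arm difference at start | Arm-by-time |
|---|---|---|---|---|
| both 12 to 4 | 0 | +0.02, 5% | +0.06, 6% | -0.01, 3% |
| both 8, constant | -1.5 | +0.01, 4% | +0.04, 4% | -0.02, 6% |
| both 12 to 4 | -1.5 | +0.31, 25% | -0.02, 3% | +0.03, 5% |
| IV 4, SC 8, constant | -1.5 | 0.00, 5% | -0.25, 7% | 0.00, 6% |
| IV 12 to 4, SC 12 | -1.5 | +0.31, 26% | +0.01, 6% | -0.31, 18% |
| IV 12 to 4, SC 12 | -3 | +0.65, 73% | +0.03, 6% | -0.64, 46% |

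The simulated trends are a little below the Step 2 figures, as expected when bolus use varies between patients. Monte Carlo error is about 1.3 points near 5% and 2.5 to 3 points at 25% to 46%.

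**Step 4: after the change.** With scheduled readings only, or with a post-bolus indicator added, rejection returns to 3% to 7% for every term in every scenario. The time and arm-by-time effects in the affected scenarios fall to within about 0.03/min of zero. In the constant-use scenario (IV 4, SC 8) the arm difference falls from -0.25 to about -0.04/min.

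**The case against.** Pooling is not stated in so many words. The bracketed frequencies could describe collection only. Mirroring outcome c could mean using scheduled times only, because outcome c leaves out the pain scores taken around boluses, and its post hoc comparisons at each time point suit common nominal times. This is fair: the wording leaves room for it. But the sentence names both kinds of reading as what the model will assess, and nothing elsewhere restricts them, so pooling remains the plainer reading.

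A reader might go further and infer that the model must produce a trend and a route difference whatever the data. The document does not support that. The artefact needs a post-bolus level that differs, together with bolus use that changes over time or differs by arm. The SAP states none of these as fact. Unequal bolus numbers are an alternative hypothesis with a matching null in section 2.4.1.1, and a fall in use during titration is nowhere asserted. Equal but declining use distorts the time trend only, and a constant arm difference in use had little effect on error rates (7%).

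Two further limits stand. The rates and shifts are assumptions, and only respiration was simulated; the mechanism carries over to sedation, but its size there is unknown. Scheduled readings are also not free of bolus influence, since section 4.6.1.3 requires more than 2 hours since the last bolus before assuming steady state. Restricting to them stops bolus use from deciding when readings are taken; it does not isolate a bolus-free level.

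**Conclusion.** The concern holds in conditional form. As written, section 5 most plainly pools readings of two kinds under a model that cannot separate them, and false effects can follow. Under the assumptions above, the false arm-by-time effect is about 0.3 to 0.6 breaths/min over 48 h, significant in 18% to 46% of trials. The false time trend is of similar size and is significant in 25% to 73%. If post-bolus readings do not differ, or bolus use is constant and equal between arms, there is no bias.

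The scope is narrow: a safety analysis, plus exploratory question v for respiration frequency (that question does not cover sedation). The primary outcome, the secondary outcomes and the 12-hourly saturation analysis are unaffected. It is still worth correcting, because the remedy is a change of wording made before analysis.

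**What to change.** In section 5, choose one of the following and state it:

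- Fit the main mixed model for respiration frequency and sedation level to the scheduled 2-hourly readings only, and summarise post-bolus readings separately by route. Cost: fewer readings in the trend model, with about 24 per patient remaining.
- Keep all readings and add a term for reading type, or for time since the last bolus. Cost: one extra model term. A single term assumes the same post-bolus shift in both arms, as my simulation did; if that is doubtful, let the term differ by route.

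The first is simpler to interpret, since it describes levels at times that bolus use does not determine.

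Also reconcile the reading schedule in section 5 (2-hourly and after each bolus) with Table 1 (baseline, 12, 24, 36 and 48 hours for vital signs, with sedation level and respiratory rate in the footnote), so that it is clear which readings count as scheduled. None of this needs new data.

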### 4.6.5 Assumption Checks and Alternative Analyses

Assumptions for independent sample t-test (normality and homoscedasticity) and linear mixed models (homoscedasticity and normality of residuals) will be assessed by standard methods.

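### With a polynomial time trend, the 12-hourly pain-score model leaves short-range correlation in the 2-hourly sedation and respiration readings unmodelled, and its group-by-time test becomes too liberal

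*SAP*

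**What the plan says.** Section 5 (Safety Analyses) lists the study-specific safety measurements: "Repeated measurement of saturation (every 12 hours), sedation level and respiration frequency (every 2 hour and after each bolus dose". It states that these "will be assessed by linear mixed models mirroring the approach used for the analysis of secondary outcome c".

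The model for outcome c, the pain score, is in section 4.6.1.1: "Linear mixed model with random effects for patients and slopes will be estimated to assess the difference between the groups in overall trend". Its fixed part contains "fixed effects for (possibly non-linear polynomial for) time, group dummy and the interaction between the two". Between-group comparisons at each time point follow as post hoc analyses. Section 4.1.1 places the pain scores at 0, 12, 24, 36 and 48 hours.

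No residual correlation structure is named for either schedule. Section 4.6.5 says that the assumptions of "linear mixed models (homoscedasticity and normality of residuals) will be assessed by standard methods". Section 4.6.7 says that a transformation or robust errors will be considered if larger deviations from the model assumptions are found. Section 2.4.2 treats two-sided p-values below 0.05 as significant.

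**The concern.** Outcome c gives 48/12 + 1 = 5 scores per patient. The safety schedule gives 48/2 + 1 = 25 scheduled readings per patient, plus those after each bolus. Two respiratory rates taken 2 hours apart are likely to resemble each other more than the patient's own level and straight line explain. A random intercept and slope absorb the long-range part of this resemblance but not the short-range part.

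If time is a straight line, this does little harm to the group-by-time test. If the fixed part is curved and the random part is not, the group-by-time-squared and higher terms are judged against a within-patient error that treats the 25 readings as independent. That error is too small for slow curvature.

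At stake is whether a route difference in respiratory or sedation trend is reported when none exists. Respiration by route is an exploratory research question (section 1.3.2, item v), and both measures are the trial's own study-specific safety readings.

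**Working it through.** **Inputs from the SAP.** There are 30 patients per arm, 23 of them expected to be evaluable (section 4.9). Readings are 2-hourly over 48 hours, and the two-sided significance level is 0.05. The model is as in 4.6.1.1. The SAP states no error rate for the safety models, so the only figure to reproduce is the sample size. For a 12 h difference and an SD of 12 h, the noncentral t gives power 0.8997 at 22 per arm and 0.912 at 23. This confirms 23.

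**Assumptions not in the SAP.** There is no route difference. Serial errors within a patient have correlation ρ between readings 2 h apart, decaying as ρ^|j−k|, with ρ from 0.3 to 0.7. Data are balanced and complete. The fitted model has independent residuals and a linear random slope only.

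**Step 1: straight-line time.** The random slope lets the model estimate the between-patient variance of the slopes directly. In balanced data the group-by-time test is therefore in effect a t-test on patient slopes. Simulated error is 5.0-5.7% for ρ from 0.3 to 0.8.

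**Step 2: the squared term.** Let p be the unit-length quadratic orthogonal polynomial over the 25 times, C the serial covariance matrix, and M the projection that removes level and slope.
- True variance of a patient's curvature score: p′Cp.
- Variance the model gives it: tr(MC)/23, the average over the 25 − 2 remaining directions.
- Ratio r = p′Cp ÷ [tr(MC)/23].
- False-positive rate of this single term: P(|Z| > 1.96/√r).

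| ρ | r | 1.96/√r | Single squared term |
|---|---|---|---|
| 0.3 | 1.73 | 1.49 | about 14% |
| 0.5 | 2.61 | 1.21 | about 23% |
| 0.7 | 4.23 | 0.95 | about 34% |

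**Step 3: joint group-by-time test.** The joint test combines the well-calibrated linear term with the liberal higher terms. The table gives the range over repeated simulations (closed-form balanced REML, 3,000 or more trials per setting in those with a recorded run count).

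| ρ | Quadratic | Cubic |
|---|---|---|
| 0 | 5-6% | 5-6% |
| 0.3 | 11-12% | 14-15% |
| 0.5 | 18-21% | 25-27% |
| 0.7 | 29-31% | 40-43% |

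Iteratively fitted mixed models with quadratic time (400 fits per setting) gave 13%, 20% and 30% at ρ = 0.3, 0.5 and 0.7.

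**Step 4: measurement noise.** Independent noise dilutes the serial part. With noise variance one quarter of the serial variance, the quadratic test gives about 17% at ρ = 0.5 and 25% at 0.7. With the two variances equal it gives about 11% and 17%. An intermediate figure is 14% and 21%.

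**Step 5: the 12-hourly schedule.** The correlation between adjacent readings falls to ρ^6, for example 0.5^6 = 0.016 and 0.7^6 = 0.118. The quadratic joint test then gives 5-7%. The inflation therefore comes from moving the model to the dense schedule.

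**Step 6: remedies.** Random coefficients for all polynomial terms give 4-6%. Patient-clustered variance gives 5-7% with a chi-square reference (up to 7.4% at 23 per arm) and 5-6% with a small-sample F. The correct serial covariance, taken as known, gives 5-6%.

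**The case against.** A reader might infer that the planned test is wrong in 13-30% of trials whatever is fitted, or that the model ignores correlation altogether. The SAP supports neither. A polynomial is only a possibility in 4.6.1.1, straight-line time keeps the error near 5%, and the intercept and slope do absorb part of the correlation. The 400-fit run that showed 7.8% for straight-line time was too small to be informative, and larger runs give 5.0-5.7%.

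The SAP also never says that residuals are independent or that the random slope is linear only. Both are the natural default reading, not stated text. Random coefficients for each polynomial term would fit the wording and would remove the problem. This stands, and it is a reason to write the choice down.

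The form of time may be chosen from the data, and this does not rescue the test. In simulation with no true trend, the quadratic was used if either squared term was significant and the line otherwise. That rule gave 13%, 20% and 31% false route differences at ρ = 0.3, 0.5 and 0.7, against 7.6% with no correlation.

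Robust errors are available under 4.6.7, and serial dependence could count as a larger deviation. But they are only to be considered, and the two named residual checks can both pass when errors are serially correlated.

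Table 1 (section 2.5) schedules vital signs, with respiratory rate and sedation level in its footnote, at baseline and every 12 hours. If only those visits were analysed, the error would be 5-7%. Section 5, however, ties the mixed model to the 2-hourly readings, and section 5.3 refers back to section 5 for respiration.

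Finally, no decision rule in the SAP depends on these p-values, and error control across the safety analyses is not claimed. That limits the consequence but does not make the p-values correct.

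**Conclusion.** The point holds conditionally. It requires three things together: a polynomial time trend, a random part with only a linear slope, and residual correlation between readings 2 hours apart. The SAP allows the first, is most naturally read as having the second, and does not address the third.

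Under the stated assumptions the joint group-by-time test at nominal 5% rejects in about 11-30% of null trials with quadratic time and about 14-42% with cubic time. With measurement noise added, the quadratic figure is about 14-21% at correlation 0.5-0.7, depending on how much noise there is. The correlations are assumed, not taken from the SAP. The simulations leave out the post-bolus readings, missing data and the ordinal nature of sedation scores.

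The consequence is misleading p-values for safety trends. The primary comparison, the sample size and adverse event reporting are untouched. The change is worth making because it is cheap and because the named checks would not reveal the fault.

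**What to change.** In section 5, replace the plain reference to outcome c for the 2-hourly measures with a statement that does two things:

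- fixes the form of time in advance;
- specifies one of the following: a random coefficient for every polynomial time term in the fixed part, a residual correlation that decays with the time between readings, or patient-clustered standard errors with a small-sample reference distribution.

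Add residual autocorrelation to the checks in 4.6.5. It would also help to say which readings enter the model, given the 12-hourly vital signs in Table 1.

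The cost is a sentence or two in the SAP and one model option. Confidence intervals for the safety trends become somewhat wider. For the squared term under the noise-free assumptions above, the factor is √r, from √1.73 = 1.3 to √4.23 = 2.1. That is the width those intervals should have had, and the linear term is essentially unchanged.

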**Table 2 Baseline characteristics**

Characteristics	IV (n=xx)	SC (n=xx)	Overall (n=xx)
Age, mean/median (SD, min-max)/(min-max,Q 1 -Q 3 )			
Sex Female, n (%)			
Performance status Karnofsky, median (min-max, Q 1 -Q 3 )			
ESAS, baseline For each element mean (SD, min-max)			
EORTC-QLQ c 30, baseline Function, mean (SD, min-max)			
Global health, mean (SD, min-max)			
Symptom burden, mean (SD, min-max)			
Weight, mean (SD, min-max)			
Height, mean (SD, min-max)			
BMI, mean (SD, min-max)			
Years with principal cancer diagnosis, median (min-max,Q 1 -Q 3 )			
Metastatic situation	n (%)	n (%)	n (%)
Localized/locally advanced disease only			
Metastatic disease			
Cancer diagnosis	n (%)	n (%)	n (%)
Malignant neoplasms of digestive organs			
Malignant neoplasms of respiratory and intrathoracic organs			
Malignant neoplasms of urinary tract			
Malignant neoplasms of male genital organs			
Malignant neoplasm of breast			
Malignant neoplasms of female genital organs			

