#### **4.1.4 Opioid side effect score**

A questionnaire used to rate the intensity of 10 common symptoms experienced when on opioid treatment, including nausea, vomiting, constipation, drowsiness, disorientation, hallucinations, and spasticity on an 11-point numeric rating scale mimicking the NRS scale will be used (Fallon et al., 2022)

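### The plan asks how the opioid side effect score changes from 0 h, but it reports and tests only the 24 h and 48 h levels

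*SAP*

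**What the plan says.** Section 1.3.2 lists as exploratory question vi: "What is the change in opioid side effect score in the two groups at 0, 24 and 48 hours". Table 1 has a row for "Opioid side effects", marked at baseline/start of treatment and again at 24 and 48 hours, so a 0 h value is collected. Section 4.1.4 describes the instrument ("A questionnaire used to rate the intensity of 10 common symptoms experienced when on opioid treatment") but gives no analysis.

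The analysis is one sentence in section 5: "Opioid side effects score, mean (SD) at 24 and 48 hours will be presented for each treatment group and compared" by an independent samples t-test. The sentence before it deals with oxygen saturation, sedation level and respiration frequency, which "will be assessed by linear mixed models mirroring the approach used for the analysis of secondary outcome c". For outcome c that approach (section 4.6.1.1) includes this step: "Post hoc analyses will be performed to assess between-group differences at each time point as well as within-group changes". It is not extended to the side effect score.

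Table 2 has a row for "ESAS, baseline For each element mean (SD, min-max)" and rows for baseline EORTC QLQ-C30, but none for the opioid side effect score.

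**The concern.** The question is about change and names 0 h as one of its time points. The analysis is about levels and leaves 0 h out. Patients enter the trial already on oral or transdermal opioids (section 1.2), so they may have opioid side effects before the first infusion. A mean at 48 h cannot then show whether symptoms rose, fell or stayed the same after the switch to parenteral morphine. Levels at 24 h and 48 h give at most the change between those two times.

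There is also a loss of precision. A baseline measurement of the same score is collected and then not used in the between-arm comparison, in a trial of 23 to 30 patients per arm.

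**Working it through.** **Where the 0 h score is used**

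| Place in SAP | Treatment of the opioid side effect score |
|---|---|
| 1.3.2, question vi | Change over 0, 24 and 48 h, in the two groups |
| Table 1 | Collected at baseline, 24 h and 48 h |
| Table 2 | Not listed, although baseline ESAS and QLQ-C30 are |
| 4.1.4 | Instrument described, no analysis |
| 5 | Mean (SD) at 24 h and 48 h, t-test between arms |

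The 0 h value is collected and then used nowhere. Change from 0 h needs that value, so the planned output cannot supply it.

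**Size of the precision loss**

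The SAP states no figure to reproduce here. Inputs: n = 23 per arm (minimum) and 30 per arm (enrolled), both from section 4.9, so N = 2n = 46 or 60. The correlation r between the 0 h score and a later score is not given; 0.1, 0.3, 0.5 and 0.7 are assumed. Equal variance at 0 h and follow-up is also assumed for the change score.

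Variance relative to the planned t-test on levels:

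- ANCOVA, large sample: 1 − r².
- ANCOVA, allowing for chance baseline imbalance: (1 − r²)(N − 3)/(N − 4). The factor is 43/42 = 1.0238 for N = 46 and 57/56 = 1.0179 for N = 60.
- Raw change score: 2(1 − r).

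The ratio of 95% CI widths, ANCOVA to level test, is the square root of the finite-sample variance ratio times t(0.975, N − 3)/t(0.975, N − 2).

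| r | ANCOVA, large sample | ANCOVA, N = 46 | ANCOVA, N = 60 | CI width ratio, N = 46 | CI width ratio, N = 60 | Raw change score |
|---|---|---|---|---|---|---|
| 0.1 | 0.99 | 1.014 | 1.008 | 1.007 | 1.004 | 1.80 |
| 0.3 | 0.91 | 0.932 | 0.926 | 0.966 | 0.963 | 1.40 |
| 0.5 | 0.75 | 0.768 | 0.763 | 0.877 | 0.874 | 1.00 |
| 0.7 | 0.51 | 0.522 | 0.519 | 0.723 | 0.721 | 0.60 |

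Worked cell, N = 46 and r = 0.5: 0.75 × 1.0238 = 0.768 for the variance, and a CI width ratio of 0.877. A simulation of 40,000 trials for this cell gave 0.771 and 0.877. It also confirmed that the difference in levels is centred on the true value.

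At r = 0 the ANCOVA interval is wider by a factor of 1.0125 (N = 46) or 1.0093 (N = 60). The two methods give equal width at r of about 0.16 (N = 46) or 0.14 (N = 60). A raw change-score t-test is less precise than the level test when r is below 0.5, and less precise than ANCOVA at every r shown.

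**The case against.** Randomisation makes the t-test on levels a valid comparison between arms. Choosing ANCOVA is therefore a matter of efficiency, and the gain depends on an r that the SAP does not give. That stands: the precision figures are conditional and do not show that the planned test is wrong. They also describe one score with one r; if the ten items are analysed separately, each has its own r and may be skewed. But validity between arms does not answer a question about change within them.

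Second, the data are collected, several other exploratory questions have no stated method, and section 4.8 sends unspecified analyses to a separate plan. So nothing is irretrievably lost. This is true, and it limits the severity. It does not remove the mismatch: this score does have a specified analysis, and that analysis does not fit the listed question.

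Third, ESAS covers nausea and drowsiness from baseline onwards. It is a different instrument, however, and does not list vomiting, constipation, disorientation, hallucinations or spasticity.

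Fourth, the outcome c mixed model could be extended to this score, or question vi could be reworded. Extending the model would give the within-group changes. As specified it has a free group effect at 0 h, so its between-arm differences would not condition on the 0 h score. Rewording would make the text consistent but leave a collected baseline unused.

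**Conclusion.** The concern holds and is minor. Followed as written, the SAP leaves a listed exploratory question unanswered although its data are collected. This part rests on the text alone and needs no assumption.

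The between-arm comparison is unbiased but probably less precise than it could be. ANCOVA gives the narrower interval once r exceeds about 0.16 (23 per arm) or 0.14 (30 per arm). At 23 per arm the interval would be about 3% narrower at r = 0.3, 12% at r = 0.5 and 28% at r = 0.7. These sizes depend on the assumed r. The primary analysis and the trial's main claim are not affected.

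**What to change.** Amend section 5 as follows.

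1. Present the opioid side effect score at 0, 24 and 48 h by arm, with the mean change from 0 h to 24 h and from 0 h to 48 h and their 95% CIs. This step alone answers question vi.
2. Replace the two t-tests by ANCOVA at 24 h and at 48 h with the 0 h score as covariate, reporting the adjusted mean difference with 95% CI. Do not use a raw change-score t-test for the comparison between arms.
3. If a 0 h score is missing, insert the mean pooled over both arms as the covariate value, so that no patient with a follow-up score is dropped.

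Apply steps 1 and 2 to the same score, and say in section 4.1.4 whether that is a total or each item, since no total is defined there. The primary t-test (section 4.4) and the outcome c model (section 4.6.1.1) stay as they are.

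The cost is SAP wording, two regression commands and a few table rows, with no new data. Each ANCOVA spends one degree of freedom. If the 0 h score turns out to be unrelated to later scores, the 95% CI is 1.3% wider at 23 per arm and 0.9% wider at 30 per arm.
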